**16**     **APPENDIX 2 – ACNE PATIENT SELF-QUESTIONNAIRE**

1. Over the past 7 days, rate how oily your face looked:

- *Asked at BL, wk 4, 8, 12, and OLE 12, 24, 36*

- Not at all oily
- Slightly oily
- Moderately oily
- Very oily
- Extremely oily

2. Over the past 7 days, rate how your face looked overall as the result of your acne:

- *Asked at BL, wk 4, 8, 12, and OLE 12, 24, 36*

- |                          |                          |                          |                          |                          |                          |                          |                          |                          |                          |                          |
|--------------------------|--------------------------|--------------------------|--------------------------|--------------------------|--------------------------|--------------------------|--------------------------|--------------------------|--------------------------|--------------------------|
|  |  |  |  |  |  |  |  |  |  |  |
| 0                        | 1                        | 2                        | 3                        | 4                        | 5                        | 6                        | 7                        | 8                        | 9                        | 10                       |
| Bad                      |                          |                          |                          |                          |                          |                          |                          |                          |                          | Excellent                |

3. Overall, how would you rate your acne now as compared to before starting the study treatment?

- *Only asked at wk 4, 8, 12, and OLE 12, 24, 36*

- Very much improved
- Moderately improved
- No difference
- Moderately worse
- Very much worse

4. Over the past 7 days, how self-conscious did you feel about the way your face looks because of your facial acne?

- *Asked at BL, wk 4, 8, 12, and OLE 12, 24, 36*

1. Not at all self-conscious
2. Slightly self-conscious
3. Moderately self-conscious
4. Very self-conscious
5. Extremely self-conscious

5. Over the past 7 days, how insecure did you feel about the way your face looks because of your facial acne?
  - *Asked at BL, wk 4, 8, 12, and OLE 12, 24, 36*
    1. Not at all insecure
    2. Slightly insecure
    3. Moderately insecure
    4. Very insecure
    5. Extremely insecure
  
6. Over the past 7 days, how often did you avoid interactions with other people because of your facial acne?
  - *Asked at BL, wk 4, 8, 12, and OLE 12, 24, 36*
    1. Never
    2. Rarely
    3. Some of the time
    4. Most of the time
    5. All of the time
  
7. Over the past 7 days, how embarrassed were you by the way your face looked because of your facial acne?
  - *Asked at BL, wk 4, 8, 12, and OLE 12, 24, 36*
    1. Not at all embarrassed
    2. Slightly embarrassed
    3. Moderately embarrassed
    4. Very embarrassed
    5. Extremely embarrassed
  
8. Over the past 7 days, how sad were you by the way your face looked because of you facial acne?
  - *Asked at BL, wk 4, 8, 12, and OLE 12, 24, 36*
    1. Not at all sad
    2. Slightly sad
    3. Moderately sad
    4. Very sad
    5. Extremely sad

On a scale of 1 to 5 (1 = *Very unsatisfied*, 5 = *Very satisfied*), how satisfied were you with each of the following?

- *To be asked just at wk 12*

	1 – Very Unsatisfied	2 – Unsatisfied	3 – Neutral	4 – Satisfied	5 – Very Satisfied
9. Ease of product application					
10. How the product looks on my skin at time of application					
11. How the product feels on my skin while applying					
12. How well the product fits into my daily skin care routine					

## 1. LIST OF ABBREVIATIONS AND DEFINITIONS OF TERMS

AE(s)	adverse event(s)
BID	twice daily
DRM01B-ACN03	ACN03
DRM01B-ACN04	ACN04
DRM01B-ACN05	ACN05
ECG	electrocardiogram
eCRF(s)	electronic case report form(s)
ET	early termination
ICF	informed consent form
IGA	Investigator's global assessment
ITT	intent-to-treat
LSR(s)	local skin reaction(s)
MedDRA	Medical Dictionary for Regulatory Activities
PI	Principal Investigator
QD	once daily
SAS®	Statistical Analysis System (SAS® Institute Inc., Cary, NC)
SOC	system organ class
TEAE(s)	treatment-emergent adverse event(s)

## 2. INTRODUCTION

Acne arises from a combination of physiological changes in the skin including altered sebaceous gland cell differentiation, heightened sebum production, localized bacterial colonization and inflammation. Although acne is generally viewed as a benign dermatological disease of adolescence, more severe forms may lead to permanent scar formation, with some of these patients suffering from psychological injury and significant loss of self-worth. Recent scientific advances in the understanding of the complex multi-factorial nature of this common disease offer great opportunity for scientific innovation through selective targeting of key elements of the disease process.

Topical agents routinely prescribed for acne, including antibiotics, retinoids and combinations thereof, often produce only modest therapeutic benefits and do not affect sebum production. A locally-delivered medication that selectively inhibited sebum formation would represent a breakthrough advance in reducing the pathogenic influences of sebum overproduction in acne.

Dermira, Inc. is pursuing the development of olumacostat glasaretil, previously referred to as DRM01B, a pro-drug of TOFA (5-(tetradecyloxy)-2-furancarboxylic acid), sarcosine ester, as a topically applied sebum inhibitor for the treatment of acne vulgaris. Olumacostat glasaretil is a

new chemical entity and has been formulated for clinical development as Olumacostat Glasaretil Gel, 5.0%.

The DRM01B-ACN05 (ACN05) study described herein is an open-label study to assess the long-term safety of continuous treatment with Olumacostat Glasaretil Gel, 5% for up to an additional 36-weeks in subjects who have completed either of the DRM01B-ACN03 (ACN03) or DRM01B-ACN04 (ACN04) studies.

### **3. STUDY OBJECTIVES**

The objective of this study is to assess the long-term safety of Olumacostat Glasaretil Gel, 5.0%, in subjects with acne vulgaris.

This study may be stopped once at least 100 subjects have been treated for 36 weeks.

### **4. STUDY DESIGN**

#### **4.1 Overall Study Design**

This study is an open-label, long-term safety study enrolling up to 700 subjects who participated in either ACN03 or ACN04 studies. All subjects will sign an informed consent / assent prior to continuing in this open label study.

Eligible subjects will receive open-label treatment with Olumacostat Glasaretil Gel, 5.0% and continue to dose twice daily for 36 weeks. Subjects, who participated in ACN03 study with acne on the chest, back or shoulders and applied study drug to affected areas will be allowed to continue to apply study drug to the affected areas. Subjects who participated in ACN04 study will continue to apply study drug to the face only. Subjects will receive a phone call at Week 2 to assess safety, and will return to the clinic at Weeks 4, 8, 12, 16, 20, 24, 28, 32, and 36 (End of Study).

Efficacy will be assessed via a static evaluation of qualitative overall acne severity, the investigator's global assessment of acne (IGA).

At the Week 12 and 24 visits, if the severity of acne has become worse, as determined by the IGA, the subject should be withdrawn, at the investigator's discretion. Severity of acne will be assessed on the face only.

Safety will be assessed through adverse events, local skin reactions (LSRs), serum chemistry, hematology and urinalysis laboratory testing, ECGs, physical examination, pulse and blood pressure.

Photographs of the face will be taken for all subjects in a subset of study sites in order to assess visually, the appearance of acne vulgaris during the course of the study.

During the clinic visit, subjects will be asked to complete the Acne Patient Self-Questionnaire.

#### **4.1.1 Schedule of Visits and Assessments**

The schedule of assessments can be found in Section 8 and Appendix 1 of the protocol.

#### **4.1.2 Method of Assigning Subjects to Treatment Groups**

Subjects will maintain the unique subject number assigned at randomization into their study of origin (either ACN03 or ACN04). All subjects will receive Olumacostat Glasaretil Gel, 5.0%, BID.

#### **4.1.3 Blinding**

This is an open-label study. Subjects will not be unblinded to their treatment assignment prior to enrollment into this study (ACN05). Once enrolled, each subject will receive Olumacostat Glasaretil Gel, 5.0%.

### **5. EFFICACY AND SAFETY ENDPOINTS**

#### **5.1 Efficacy Endpoint**

The IGA of acne severity on the face only will be conducted for each subject every 12 weeks.

#### **5.2 Safety Endpoints**

Safety will be assessed through adverse events (AEs), local skin reactions (LSRs), serum chemistry, hematology and urinalysis laboratory testing, ECG testing, physical examination and vital signs.

### **6. STATISTICAL AND ANALYTICAL PLANS**

#### **6.1 General Methodology**

All statistical processing will be performed using SAS® unless otherwise stated. Data will be summarized using descriptive statistics. No inferential testing or imputations for missing data will be performed.

Categorical variables will be tabulated with frequencies and percentages. Continuous variables will be tabulated with mean, median, SD, and range (minimum and maximum).

Reported AEs and prior and concomitant procedures and therapies will be classified on the basis of Medical Dictionary for Regulatory Activities (MedDRA) terminology. Concomitant medications will be classified on the basis of World Health Organization Drug Dictionary (WHO-DDE) terminology.

The following data will be imported from ACN03/ACN04 (Baseline defined in section 6.1.2):

Subjects receiving Olumacostat Glasaretil Gel, 5.0% in ACN03/ACN04:

- Demographic information: age, gender, race and ethnicity
- Prior and Concomitant medications
- Adverse events
- Local skin reactions (Baseline and Weeks 4, 8, 12)
- Vital signs and weight (Baseline and Weeks 4, 8, 12)
- Investigator Global Assessment of acne (Baseline and Week 12)
- Acne Patient Self-Questionnaire (Baseline and Week 12)
- Laboratory evaluations: hematology, serum chemistries and urinalysis (Baseline)
- 12-lead ECG (Baseline)

Subjects receiving Olumacostat Glasaretil Gel, Vehicle in ACN03/ACN04:

- Demographic information: age, gender, race, and ethnicity
- Prior and Concomitant medications
- Adverse events
- Local skin reactions (Baseline)
- Vital signs and weight (Baseline)
- Investigator Global Assessment of acne (Baseline)
- Acne Patient Self-Questionnaire (Baseline)
- Laboratory evaluations: hematology, serum chemistries and urinalysis (Baseline)
- 12-lead ECG (Baseline)

### **6.1.1 Statistical Analysis**

All analyses will be performed by QST using SAS® Version 9.3 or later. All summary tables and data listings will be prepared utilizing SAS® software.

The standard operating procedures (SOPs) of QST will be followed in the creation and quality control of all data displays and analyses.

### **6.1.2 Baseline Definition**

The baseline value for each parameter will be defined as the last observation prior to first dose of Olumacostat Glasaretil Gel, 5.0%. For subjects receiving Olumacostat Glasaretil Gel, 5.0% in ACN03/ACN04, the baseline values from ACN03/ACN04 will be considered the baseline values for calculations in ACN05. For subjects receiving Olumacostat Glasaretil Gel, Vehicle in ACN03/ACN04, baseline values will most commonly be from the Week 12/study exit visit of ACN03/ACN04. If subjects choose to enroll in this study, study procedures will not be repeated; study sites will carry over the information from the ACN03/ACN04 study to the Day 1 visit for this study.

**6.1.3 Visit Windowing**

For subjects receiving Olumacostat Glasaretil Gel, 5.0% in ACN03/ACN04, data from ACN03/ACN04 will be included in summaries of ACN05. For subjects receiving Olumacostat Glasaretil Gel, Vehicle in ACN03/ACN04, baseline values will be sourced from ACN03/ACN04 and data from follow-up visits of ACN05 will be used in summaries. The table below details the analysis visits to be summarized and the associated visits from ACN03/ACN04 or ACN05 which will be sourced for each type of subject.

**Analysis Visits for Efficacy and Safety Assessments**

Analysis Visit	Subjects Receiving Olumacostat Glasaretil Gel, 5.0% in ACN03/ACN04	Subjects Receiving Olumacostat Glasaretil Gel, Vehicle in ACN03/ACN04
Week 4	ACN03/ACN04 - Week 4	ACN05 - Week 4
Week 8	ACN03/ACN04 - Week 8	ACN05 - Week 8
Week 12	ACN03/ACN04 - Week 12	ACN05 - Week 12
Week 16	ACN05 - Week 4	ACN05 - Week 16
Week 20	ACN05 - Week 8	ACN05 - Week 20
Week 24	ACN05 - Week 12	ACN05 - Week 24
Week 28	ACN05 - Week 16	ACN05 - Week 28
Week 32	ACN05 - Week 20	ACN05 - Week 32
Week 36	ACN05 - Week 24	ACN05 - Week 36
Week 40	ACN05 - Week 28	Not available
Week 44	ACN05 - Week 32	Not available
Week 48	ACN05 - Week 36	Not available

Note: analysis visits from ACN03/ACN04 will be utilized.

Data from ACN05 will be mapped to the appropriate analysis visit described above based on nominal visit indications. The nominal visit for vital sign and LSR data from early termination (ET) and unscheduled visits will be determined using nominal visit windows. The nominal visit windows for ET and unscheduled visits are presented in the following table.

**ACN05 Nominal Visit Windows for Efficacy and Safety Assessments**

Nominal Visit	Target Study Day	Window (Days)
Week 4	29	22 to 42
Week 8	57	43 to 70
Week 12	85	71 to 98
Week 16	113	99 to 126
Week 20	141	127 to 154
Week 24	169	155 to 182
Week 28	197	183 to 210
Week 32	225	211 to 238
Week 36	253	239 to 266

Data collected at ET and unscheduled visits prior to study day 22 will not be analyzed. Data collected at ET and unscheduled visits after study day 266 will not be included in analyses.

The definition for the study day included in each study window is defined as below:

$$\text{Study Day prior to Day 1} = \text{Visit Date} - \text{Day 1 Date}$$

$$\text{Study Day on or after Day 1} = \text{Visit Date} - \text{Day 1 Date} + 1$$

If an assessment's mapped nominal visit is a visit at which the subject has data from a scheduled visit present, or if no analyses are planned for the assessment at the mapped nominal visit, the data collected at the ET or unscheduled visit will not be included in analyses.

In the event of multiple values from unscheduled or ET assessments within a nominal visit window, the value closest to the scheduled visit target study day will be used for analyses. If two values tie as closest to the time point (for example, one value is before and the other value is after the time point), then the later value will be selected.

Other data summaries will include information collected at ET visits as Week 36/ET.

Data collected at all visits will be included in the data listings with the ACN05 analysis visit presented.

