#### **9.4.5 Local Skin Reactions**

All subjects will be assessed for LSRs, on the face, at each visit. LSRs include burning/stinging, pruritus, erythema, dryness and peeling. Each LSR will be scored as 0 (None), 1 (Mild), 2 (Moderate) or 3 (Severe) (Table 2). LSRs observed on a visit day will not be recorded as adverse events unless scored as 3 (Severe). Local skin reactions experienced by the subject in between study visits are to be recorded as an AE.

Burning/stinging and pruritus will be assessed by the subject and erythema, dryness and scaling will be assessed by the Investigator/designee (Table 3). Subjects will be read the definition of each subject-assessed LSR and asked to select the appropriate definition. The corresponding grade will be assigned by the site and entered in the eCRF.

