#### **6.8.4.4 Local Skin Reactions (LSRs)**

Local Skin Responses (LSRs) include erythema, peeling, dryness, burning/stinging and pruritus. These will be scored as 0 (None), 1 (Mild), 2 (Moderate) or 3 (Severe). LSRs will be summarized by analysis visit using descriptive statistics. Specifically, analysis visits to be summarized include Baseline and Weeks 4, 8, 12, 16, 20, 24, 28, 32, 36, 40, 44, 48. Each subject's worst post-baseline grade for each LSR will also be summarized. Additionally, the number of subjects who experience mild, moderate or severe LSRs post-baseline will be presented. By-subject listings of all LSRs, as well as subjects with any severe LSRs will be included.

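### The SAP's visit-window exclusions also reach the worst-grade and severity summaries of local skin reactions, so they can only understate the worst grade observed

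*SAP*

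**What the plan says.** SAP 6.1.3 (Visit Windowing) names LSRs explicitly: "The nominal visit for vital sign and LSR data from early termination (ET) and unscheduled visits will be determined using nominal visit windows". Four rules follow under the ACN05 window table:

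- Early values: "Data collected at ET and unscheduled visits prior to study day 22 will not be analyzed".
- Late values: ET and unscheduled data after Day 266 are left out.
- Occupied windows: if the subject already has scheduled data at the mapped visit, "the data collected at the ET or unscheduled visit will not be included in analyses".
- Several ET or unscheduled values in one window: "the value closest to the scheduled visit target study day will be used for analyses", with ties going to the later value.

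The one clear exception is for data listings, which keep all visits.

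SAP 6.8.4.4 plans by-visit LSR statistics and two summaries that are not by visit. Each subject's "worst post-baseline grade for each LSR will also be summarized", and "the number of subjects who experience mild, moderate or severe LSRs post-baseline will be presented". It does not say which records feed those two.

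The protocol has LSRs assessed at each visit (9.4.5) and lists them among the ET visit procedures (8.5 and Appendix 1). Unscheduled visits exist for subjects with adverse events (8.6).

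**The concern.** Choosing one value per window is sensible when each subject should contribute once to each visit column. It is the wrong basis for a subject-level maximum, whose purpose is to show the worst thing seen at any time. Read as written, the rules have three effects on the worst-grade and severity summaries:

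1. A subject with scheduled data at every visit contributes no unscheduled LSR value at all.
2. An ET value is dropped if the subject has already had the scheduled visit in that window, although LSRs are required at the ET visit.
3. Every ET or unscheduled value on Days 2 to 21 is dropped. No scheduled clinic visit falls in that period, since Week 2 is a phone call. For subjects who had vehicle in the parent study, these are the first three weeks on active gel.

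The discarded visits are plausibly informative, because subjects come in unscheduled or leave early for a reason. Long-term safety is the study's only stated objective, and LSRs are a named safety endpoint (SAP 5.2).

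The outputs could also disagree. A grade 3 reaction at an excluded visit would appear in the severe-LSR listing and as an adverse event, but not in the worst-grade table.

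**Working it through.** **The plan's own figures.** The window table in SAP 6.1.3 reproduces exactly:

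- Target day = 7 × week + 1, giving 29, 57, …, 253.
- Lower bound = midpoint with the previous contact. For Week 4, with the Week 2 call on Day 15, (15 + 29)/2 = 22.
- Upper bound = day before the next midpoint. For Week 4, (29 + 57)/2 − 1 = 42.
- The last bound is 253 + 13 = 266.

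All nine rows match.

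**Direction.** The retained records are a subset of the observed records, and the maximum over a subset cannot exceed the maximum over the whole. Each subject's analysed worst grade is therefore lower than or equal to the observed one, or missing. Constructed examples, one for each rule:

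| Records | Observed worst | Analysed worst | Rule |
|---|---|---|---|
| Prior-vehicle subject, only an ET visit on Day 15, grade 3 | 3 | none | before Day 22 |
| Week 4 scheduled grade 1; unscheduled Day 36 grade 3; Week 8 scheduled grade 1 | 3 | 1 | window occupied |
| Week 4 scheduled grade 1; Week 8 missed; unscheduled Day 56 grade 1 and Day 65 grade 3 | 3 | 1 | closest to Day 57 |
| Week 36 scheduled grade 1; unscheduled Day 270 grade 2 | 2 | 1 | after Day 266 |

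The first subject could enter the Safety Population on that single post-baseline assessment (SAP 6.4.1) and still supply no LSR value.

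**How many ET days lose their value.** Assume every scheduled visit before the ET day was attended. Possible ET days run from Day 2 to the day before the Week 36 visit, less the 8 earlier scheduled visit days. An ET value is excluded if it falls before Day 22, or after the scheduled visit in the same window.

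| Scheduled visits | Excluded | Kept | Total | Share excluded |
|---|---|---|---|---|
| On target | 20 + 8 × 13 = 124 | 7 + 8 × 14 = 119 | 243 | 51% |
| 4 days late | 20 + 8 × 9 = 92 | 11 + 8 × 18 = 155 | 247 | 37% |
| 4 days early | 20 + 8 × 17 = 156 | 3 + 8 × 10 = 83 | 239 | 65% |

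For ET before the Week 4 visit, the excluded share is 20/27 = 74% on target, 20/31 = 65% if that visit is 4 days late, and 20/23 = 87% if it is 4 days early.

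**Unscheduled visits.** None is used for a subject with all scheduled data. In any case at most 9 ACN05 values per LSR after Day 1 can enter, one per window, however many were taken.

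**The case against.** - **The exclusions may be meant only for by-visit tables.** The section is about assigning data to analysis visits, and 6.8.4.4 describes the two summaries as post-baseline with no visit term. A programmer could reasonably use all records. But the text of 6.1.3 speaks of analyses in general and clearly spares only listings. Its sentence about other data summaries taking ET visits as Week 36/ET reads most naturally as covering other data types, and even a broad reading would restore ET values only.
- **Adverse-event tables fill the gap.** They fill part of it. Protocol 9.4.5 makes a visit-day grade 3 an adverse event and records reactions experienced between visits as adverse events with no grade limit. The treatment-emergent tables (SAP 6.8.2) use no visit windows, so a reaction that prompted an unscheduled visit should be captured there. What remains is the grade 1 or 2 reaction seen only on the excluded visit day, because "LSRs observed on a visit day will not be recorded as adverse events unless scored as 3 (Severe"). It reaches the listings but neither set of summary tables.
- **Understatement is certain only for the per-subject worst grade.** This stands. If the severity counts classify subjects by worst grade, the mild count can rise as severe cases move down. Percentages can shift either way if subjects without an analysable value leave the denominator.
- **The day shares overstate the loss.** They are not subject shares, and they assume earlier visits were attended. If the scheduled visit in the ET window was missed, the ET value is kept, and only Days 2 to 21 are lost: 20 of the 251 days before Day 253 (8%). Withdrawals for worsening at the Week 12 and 24 visits (Protocol 9.3.1) may have ET procedures on that same day, with no separate value to lose.
- **Reach is limited.** Prior-active subjects already bring parent-study LSRs at Weeks 4, 8 and 12, so the loss in the first three weeks on active gel concerns prior-vehicle subjects.

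**Conclusion.** The concern holds: the SAP is wrong as written on this point and should be changed. Following its stated rules lowers the worst LSR grade of some subjects and raises it for none. The direction is certain. The size is not known, because the documents give no rate of ET or unscheduled visits. The 51% (37% to 65%) shows only that, for a subject attending as scheduled, losing an ET value is a common outcome of the rule. ET values in a window without scheduled data are kept, Day 1 values are used, and nothing is lost from the listings. The damage is confined to the worst-grade and severity summaries, where grades 1 and 2 seen only on an excluded visit day have no adverse-event backstop.

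**What to change.** 1. In SAP 6.8.4.4, add a sentence: the worst post-baseline grade and the mild, moderate and severe counts use every LSR assessment after the first dose of active gel, whether scheduled, unscheduled or ET, on any study day.
2. In SAP 6.1.3, limit the windows and the exclusions to by-visit tables.
3. State whether unscheduled parent-study LSRs count for prior-active subjects. SAP 6.1 currently imports their LSRs only at Baseline and Weeks 4, 8 and 12.
4. Optionally, clarify that the Day 22 and Day 266 limits do not apply to the Week 36/ET and Week 48/ET summaries of laboratory, ECG and IGA data.

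Vital signs need no change, since SAP 6.8.4.2 plans only by-visit statistics. The cost is a few sentences and minor programming, because the ACN05 values are already collected and listed. The LSR table may look less favourable.
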